### **3.2. Subject Grouping**

For analyses based on the All Randomized Analysis Set or the FAS, subjects will be grouped by randomized treatment. For other analyses, subjects will be grouped by actual treatment received. The actual treatment received will differ from the randomized treatment only when the actual treatment received differs from randomized treatment for the entire treatment duration.

Subjects who received placebo in different cohorts will be combined as one placebo group for analysis purposes if applicable. The treatment groups for analysis are defined as follows:

- Treatment 1: VES 1 mg (in Cohort 1)
- Treatment 2: VES 2 mg (in Cohort 2)
- Treatment 3: VES 4 mg (in Cohort 3)
- Treatment 4: VES 6 mg (in Cohort 4)
- Treatment 5: VES 8 mg (in Cohort 5)
- Treatment 6: VES 10/12 mg (in Cohort 6)
- Treatment 7: Placebo (in all Cohorts)

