Safety: AEs and clinical laboratory tests will be collected at every visit and summarized through Day 101 or Day 157 (30 days after the last dose of GS-9620 or placebo).

The following are DLTs:

- ALT elevation defined as:
 - $ALT \geq 10 \times ULN$ **OR**
 - confirmed ALT elevation (i.e. grade shift or $2 \times$ previous value) with evidence of worsened hepatic function (e.g. total bilirubin > 2 mg/dL above Baseline, serum albumin > 1 g/dL decrease from Baseline)
- A confirmed \geq Grade 3 AE considered by the investigator to be study drug-related

- A confirmed \geq Grade 3 lab abnormality considered by the investigator to be study drug-related and clinically significant
- A persistent (≥ 72 hours) \geq Grade 2 flu-like symptom (eg pyrexia, fatigue, myalgia, arthralgia, headache, chills) considered by the investigator to be study drug-related
- A post-dose increase in plasma HIV-1 RNA that fails to resolve to < 50 copies/mL within 10 days in Cohorts 1 to 3
- A post-dose increase in plasma HIV-1 RNA that fails to resolve to < 200 copies/mL within 10 days in Cohorts 4 to 9

The Investigator will notify the SEC within 24 hours of any DLT. The SEC may unblind the treatment assignment for a subject experiencing a DLT.

Study drug dosing for a subject may be discontinued if the subject receives GS-9620 and experiences one or more DLTs considered to be related to study drug.

A Dose Cohort may be discontinued if ≥ 2 out of 6 subjects receiving GS-9620 experience one or more DLTs considered related to study drug.

Statistical Methods:

Safety:

To evaluate overall safety, the incidences of treatment-emergent AEs and treatment-emergent laboratory abnormalities will be summarized by treatment group.

The proportion of subjects in each treatment group with an AE leading to premature discontinuation of study drug and proportion of subjects with serious adverse events (SAEs) will be summarized by treatment group.

Virology:

The change in plasma HIV-1 RNA and the incidence of detectable plasma HIV-1 RNA at each visit will be summarized by treatment group.

The change in plasma HIV-1 RNA SCA from pre-dose to 2 days post-dose may be explored.

The change in cell (PBMC) associated HIV-1 RNA from pre-dose to 2 days post-dose may be explored.

The change in HIV-1 reservoir measured by cell (PBMC) associated HIV-1 DNA from pre-dose to 2 days post-dose, and in Cohorts 4 to 9 by use of secondary assays using stored PBMC samples may be explored

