8.1.2. Primary Endpoint

- The primary safety endpoint is incidence of treatment-emergent SAEs and all treatment-emergent adverse events.
- The primary virology endpoint is maximum change from baseline in plasma log₁₀ HIV-1 RNA at any post-dose timepoint

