## 1.2. Study Design

This is a phase 1b, randomized, double-blinded, placebo-controlled, multi-cohort dose-escalation study with dose cohorts: Cohort 1 (1 mg Dose), Cohort 2 (2 mg Dose), Cohort 3 (4 mg Dose), Cohort 4 (6 mg Dose), Cohort 5 (8 mg Dose), Cohort 6 (three administrations of 10 mg Dose, followed by seven administrations of 12 mg Dose; Safety Evaluation Committee [SEC] review of the 10mg safety data will be required prior to dose escalating to 12mg), and optional Cohort 7

CCI

Two additional optional adaptive cohorts, Cohort 8

CCI

and Cohort 9

CCI

HIV-1 infected male and non-pregnant, non-lactating female adults who have been virologically suppressed (HIV-1 RNA < 50 copies/mL) on ART for  $\geq 12$  consecutive months prior to screening may be eligible for entry (refer to the protocol for complete inclusion and exclusion criteria). Eligible subjects are randomly assigned to 1 of the following 2 treatment groups in a 6:2 ratio for each cohort. CCI

- Cohort 1 (n = 8): Blinded VES 1 mg (n = 6) vs. Placebo (n = 2)
- Cohort 2 (n = 8): Blinded VES 2 mg (n = 6) vs. Placebo (n = 2)
- Cohort 3 (n = 8): Blinded VES 4 mg (n = 6) vs. Placebo (n = 2)
- Cohort 4 (n = 8): Blinded VES 6 mg (n = 6) vs. Placebo (n = 2)
- Cohort 5 (n = 8): Blinded VES 8 mg (n = 6) vs. Placebo (n = 2)
- Cohort 6 (n = 8): Blinded VES 10/12 mg (n = 6) vs. Placebo (n = 2)

Central randomization is used. Enrollment will initially be opened for Cohort 1 only. The SEC will review study progress, safety and virology results of enrolled subjects. After all subjects in a cohort have received at least three doses (Cohorts 1 to 3, and 6) or five doses (Cohorts 4 and 5), the SEC will review safety data from that cohort, including adverse events (AEs) and clinical laboratory results (including plasma HIV-1 RNA) before approving the next dose escalation. CCI

A cohort may be suspended if  $\geq 2$  out of 6 subjects receiving VES experience one or more dose-limiting toxicities (DLTs) considered related to study drug. Subjects will receive a total of either 6 doses in Cohorts 1 to 3, 10 doses in Cohorts 4

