### **4.2. Extent of Exposure**

A subject's extent of exposure to study drug data will be generated from the study drug administration page in the eCRF. Exposure data will be listed.

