## **7.1.6. Treatment-Emergent Adverse Events**

### **7.1.6.1. Definition of Treatment-Emergent Adverse Events**

Treatment-emergent adverse events (TEAEs) are defined as one or both of the following:

- Any AEs with an onset date on or after the study drug start date and no later than 30 days after permanent discontinuation of study drug
- Any AEs leading to premature discontinuation of study drug

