## **7.1.7. Summaries of Adverse Events and Deaths**

A brief high-level summary of TEAEs will be provided by treatment for the number and percentage of subjects who had the following: any TEAE; any TEAE of Grade 3 or above; any serious TEAE; any study drug-related TEAE; any study drug-related serious TEAE; any TEAE that led to premature discontinuation of study drug. The treatment-emergent deaths observed during the study will also be summarized and included in this table. Treatment-emergent death refers to the death occurred between the first dose date and the last dose date plus 30 days, inclusive.

Adverse event summaries will provide the number and percentage of subjects with AEs by SOC and PT, by treatment based on the Safety Analysis Set as follows:

- All AEs
- All AEs by severity
- AEs of Grade 3 or above
- All study-drug related AEs

- All SAEs
- All study-drug related SAEs
- All AEs leading to premature discontinuation of study drug

Multiple events will be counted only once per subject per treatment in each summary. An AE that starts in one treatment period and continues into the following treatment period(s) will be counted only in the period in which the AE began. Adverse events will be summarized and listed first in alphabetic order of SOC and then by PT in order of descending incidence of the pooled treatment groups within each SOC. For summaries by severity, the most severe grade will be used for those AEs that occurred more than once in an individual subject per treatment during the study.

In addition to the by-treatment summaries described above, data listings will be provided for the following:

- All AEs (with a variable indicating whether the event is treatment emergent)
- SAEs
- Deaths
- AEs leading to premature discontinuation of study drug

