#### **7.1.8. Additional Analysis of Adverse Events**

No additional analysis of adverse events is planned.

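### SAP 4.2 drops the exposure summary that Protocol 8.6.1 requires, without declaring it, although the adverse event columns cover unequal planned follow-up

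*SAP*

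**What the plan says.** **Exposure.** Protocol 8.6.1, within the Safety Analysis section, asks for exposure to be summarised by treatment group. It defines duration as weeks from first to last dose and asks for that to be summarised too. SAP 4.2 provides only this: "Exposure data will be listed". SAP 7.7 then states that the protocol-specified safety analyses are unchanged.

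**Adverse events.** Protocol 8.1.2 sets the endpoint: "The primary safety endpoint is incidence of treatment-emergent SAEs and all treatment-emergent adverse events". SAP 7.1.7 reports the "number and percentage of subjects with AEs by SOC and PT, by treatment", counting each subject once. SAP 7.1.6.1 takes onsets from the first dose and "no later than 30 days after permanent discontinuation of study drug". The Protocol Synopsis (Criteria for Evaluation) has adverse events and laboratory tests "summarized through Day 101 or Day 157 (30 days after the last dose of GS-9620 or placebo". SAP 7.1.8 closes the list: "No additional analysis of adverse events is planned".

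**Grouping.** SAP 1.2: "Subjects will receive a total of either 6 doses in Cohorts 1 to 3, 10 doses in Cohorts 4" to 6. Each cohort plans 6 active and 2 placebo subjects. SAP 3.2: "Subjects who received placebo in different cohorts will be combined as one placebo group for analysis purposes if applicable". The closing hedge is not followed by any alternative, and Treatment 7 in the same section is placebo from all cohorts.

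**The concern.** The exposure point is a direct mismatch between the two documents, and SAP 7.7 makes it an undeclared one. SAP 4.1.2 will show how many subjects completed or stopped study drug, but no planned table gives weeks on drug or doses received by group.

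That table would be useful here because planned length changes exactly between 4 and 6 mg. Every group up to 4 mg has the short schedule and every group from 6 mg has the long one, while the placebo column is half of each. A crude percentage with each subject counted once tends to rise with time at risk. A difference between low and high doses, or between either and placebo, could therefore reflect follow-up time, drug, or both. The SAP plans no covariates (3.3), no subgroups (3.4) and no further adverse event analysis (7.1.8), so no planned table separates them. At stake is the descriptive reading of the primary safety endpoint in the study report.

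**Working it through.** **1. Exposure passages side by side.** Protocol 8.6.1: summarised by treatment group, duration in weeks. SAP 4.2: listed. SAP 7.7: no changes. The first two disagree, so the third is incorrect as it stands.

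**2. Planned windows.** Last dose day = 1 + 14 × (doses − 1); window end = last dose day + 30.
- 6 doses: 1 + 14 × 5 = Day 71; 71 + 30 = Day 101.
- 10 doses: 1 + 14 × 9 = Day 127; 127 + 30 = Day 157.

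Both reproduce the protocol's own days. The ratio is 157/101 = 1.554 in days and 10/6 = 1.667 in doses. First-to-last-dose duration is 71/7 = 10.1 weeks against 127/7 = 18.1 weeks.

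**3. Pooled placebo.** 2 × 6 = 12 planned subjects, six per schedule. Mean planned window = (6 × 101 + 6 × 157)/12 = 129 days, which matches no active column.

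**4. Size of the artificial step.** The documents give no adverse event rate or time pattern for this, so both are assumed: an inert drug and 50% of subjects with a first event by Day 101. Incidence by Day 157 = 1 − (1 − 0.5)^r, where r is the ratio of cumulative hazards.

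| Assumed time pattern | r | By Day 157 | Step (points) | Subjects of 6 |
|---|---|---|---|---|
| All first events by Day 42 | 1 | 50.0% | 0 | 0 |
| Hazard halves every 28 days | 1.067 | 52.3% | 2.3 | 0.14 |
| Hazard halves every 56 days | 1.201 | 56.5% | 6.5 | 0.39 |
| Constant daily hazard | 1.554 | 66.0% | 16.0 | 0.96 |
| Constant risk per dose | 1.667 | 68.5% | 18.5 | 1.11 |

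Under constant daily hazard, pooled placebo would read (50 + 66)/2 = 58%, 8 points from each block. With 101-day incidence varied from 10% to 70%, the step under that hazard is 5 to 16 points. One subject in six is 16.7 points.

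For SAEs at an assumed 5% by Day 101: 1 − 0.95^1.554 = 7.7%, or 0.30 against 0.46 expected subjects per column of six.

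**5. Opportunity to report.** Adverse events are solicited at every visit. Post-Day-1 visits, counted from the Synopsis schedule:

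| | Cohorts 1-3 | Cohort 4 | Cohorts 5-6 |
|---|---|---|---|
| To end of study | 30 | 26 | 32 |
| Per week | 30/(101/7) = 2.1 | 26/(157/7) = 1.2 | 32/(157/7) = 1.4 |
| To Day 84 | 29 | 15 | 18 |

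**6. What a common window does.** Day 84 is the day before the scheduled Dose 7 (Day 71 + 14 = Day 85). Under constant daily hazard every group reads 1 − 0.5^(84/101) = 43.8%, so the step is 0. At the opposite extreme, with events recorded only through visits (1 − 0.5^(k/30) for k visits), the window reads 49/29/34% for Cohorts 1-3/4/5-6, against 50/45/52% over the full period. That extreme is unrealistic, since subjects are told to contact the site at once about flu-like symptoms. It does show that the window does not equalise ascertainment.

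Early stoppers: last dose on Day 43 gives 43 + 30 = Day 73; last dose on Day 57 gives Day 87, capped at Day 84.

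**The case against.** The exposure mismatch has no good defence; at most it is minor, because the listing holds the raw data.

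The case against the follow-up point is stronger, and much of it stands:
- Protocol 8.6.2 itself plans counts and percentages by treatment group. A reader might infer that the SAP departs from the protocol by using crude percentages. It does not; only the exposure summary departs.
- A reader might also infer that dose escalation is at risk. SEC review takes each cohort's own data after three or five doses (Protocol 8.9), not these columns, and SAP 7.1.7 names no test.
- The size is assumed and may be near zero. Protocol 1.4 notes that related events at 8 mg had not recurred after Dose 3. That note is blinded, covers related events only and reaches five or six doses, whereas the endpoint counts all events. Protocol 1.2.3.3 reports more Grade 2 and 3 events with 12 weeks at 4 mg, but no other dose- or duration-related finding.
- A common window is not a clean remedy. It leaves visit density unequal and omits Doses 7-10. In Cohort 6, Dose 4 waits for SEC review, and viraemia holds reset the schedule (Protocol 6.8.1), so a window that ended at Dose 7 would stretch for some subjects. A fixed calendar window avoids that stretch, but doses received within it can then differ.
- Active columns are labelled by cohort with known dose counts, and adverse events are listed by subject, so a reader could rebuild some of this by hand. The mixed placebo column is the hardest to read.

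**Conclusion.** The exposure omission stands without any assumption: SAP 4.2 falls short of Protocol 8.6.1, and SAP 7.7 says otherwise.

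The follow-up point stands as a secondary one. On schedule, dose block and follow-up length coincide, and pooled placebo matches neither block. The effect is of unknown size, about 0 to 1.1 subjects per column of six under the assumed 50% incidence and the hazard patterns above; for SAEs it is too small to see. Denser solicitation in Cohorts 1-3 may offset part of it.

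The documents do not support the stronger reading that the safety comparison is invalid, that the higher doses will necessarily look worse, or that placebo should not be pooled. They support adding what a reader needs to interpret the columns.

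**What to change.** 1. In SAP 4.2, restore a summary by treatment group of duration (weeks) and number of doses received, with placebo also shown separately for Cohorts 1-3 and Cohorts 4-6. Otherwise, declare the removal in SAP 7.7.
2. Keep the full-period adverse event tables with pooled placebo as primary, and show planned doses and follow-up in each column header.
3. Add one supplementary overall TEAE and SAE table with placebo split the same way and one calendar window for everyone: Day 1 to the earlier of Day 84 and last dose + 30 days. Footnote that doses received in the window can differ where dosing was delayed, that solicitation visits number 29/15/18 for Cohorts 1-3/4/5-6, and that Doses 7-10 are not covered.

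Cost: a few extra tables from data already collected, with all 12 planned placebo subjects kept. The supplementary table puts the groups on the same calendar window but does not equalise ascertainment, so it supports the primary tables and does not replace them.

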### **3.3. Strata and Covariates**

This study does not use a stratified randomization schedule in enrolling subjects. No covariates will be included in analyses.

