6.2.3. Baseline/Day 1 Assessments (all Cohorts)

Subjects are to arrive in a fasting state for the Baseline/Day 1 visit. Initiation of the treatment with the study drug must take place in the clinic and will be administered by blinded study staff. Fasting requirement and food/liquids consumption requirement is shown in [Table 5-1](#).

For all cohorts, subjects will remain on-site for 12 hours after the first dose for safety assessments and phlebotomy. The following evaluations are to be completed at the Baseline/Day 1 Visit:

- 6.2.3.1. Review medical history
- 6.2.3.2. Review of AEs and changes in concomitant medication

CCI

- 6.2.3.4. Symptom-directed physical examination as needed
- 6.2.3.5. Vital signs (blood pressure, pulse, respiration rate and temperature)
- 6.2.3.6. Weight
- 6.2.3.7. VAS Adherence Questionnaire to be completed by the subject. Subject is to read questionnaire by himself/herself and write/mark answers directly onto questionnaires. **(Cohorts 5 to 9 only)**
- 6.2.3.8. Urine collection for the following laboratory procedures:
 - 6.2.3.8.1. Urinalysis
 - 6.2.3.8.2. Urine pregnancy test (females of childbearing potential only). If the urine pregnancy test is positive at Baseline/Day 1, study drug will not be dispensed. The positive result will be confirmed with a serum pregnancy test. If the serum pregnancy test is positive, the subject will not be able to participate

- 6.2.3.9. Blood sample collection for the following laboratory analyses:
- 6.2.3.9.1. Chemistry profile: alkaline phosphatase, AST, ALT, total bilirubin, direct and indirect bilirubin, total protein, albumin, CPK, bicarbonate, BUN, calcium, chloride, creatinine, glucose, phosphorus, magnesium, potassium, sodium, uric acid
 - 6.2.3.9.2. Estimated glomerular filtration rate according to the Cockcroft-Gault formula for creatinine clearance
 - 6.2.3.9.3. Hematology profile: complete blood count (CBC) with differential and platelet count
 - 6.2.3.9.4. Plasma HIV-1 RNA (TaqMan[®] v2.0)
 - 6.2.3.9.5. CD4+ cell count
 - 6.2.3.9.5.1 CD8+ cell count, CD4/CD8 ratio and CD4 % (**Cohorts 5 to 9 only**)
 - 6.2.3.9.6. Serum for cytokine/soluble biomarker studies
 - 6.2.3.9.7. Whole blood ISG mRNA panel
 - 6.2.3.9.8. Cell-associated HIV-1 RNA/DNA (CAVR/CAVD) with stored PBMC.
 - 6.2.3.9.9. Plasma HIV-1 RNA Single Copy Assay with stored plasma
 - 6.2.3.9.10. Whole blood for immune cell activation (T, B, NK) and FoxP3+Treg level

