### 1.1. Study Objectives

The primary objectives of this study are as follows:

- To evaluate the safety and tolerability of escalating, multiple doses of Vesatolimod (VES [GS-9620]) in HIV-1 infected virologically suppressed adults on antiretroviral therapy (ART)
- To evaluate the virologic effect of VES as measured by changes in plasma HIV-1 RNA

The secondary objectives of this study are as follows:

- To evaluate the plasma pharmacokinetics (PK) of VES
- To evaluate the pharmacodynamics (PD) of VES as measured by changes in interferon-stimulated genes (ISGs) and serum cytokines in whole blood compared to placebo
- To evaluate effects of VES on whole blood immune cell activation (CD4 and CD8 T cell, NK cell)

The exploratory objectives of this study are as follows:

- [REDACTED]
- [REDACTED]
- [REDACTED]

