### **3.8.3. Selection of Data in the Event of Multiple Records in a Window**

Depending on the statistical analysis method, single values may be required for each day. For example, change from baseline by visit usually requires a single value.

If multiple valid, nonmissing, numeric measurements exist on the same nominal visit, records will be chosen based on the following rules if a single value is needed:

- In general, the baseline value will be the last nonmissing value on or prior to the first dosing date of study drug, unless specified differently. If multiple measurements occur on the same day, the last nonmissing value prior to the time of first dosing of study drug will be considered as the baseline value. If these multiple measurements occur at the same time or the time is not available, the average (arithmetic or geometric mean, as appropriate) of these measurements (for continuous data) will be considered the baseline value.
- For postbaseline values:
  - If there is more than one record on the selected day, the average will be taken (geometric mean for HIV-1 RNA and arithmetic mean for others), unless otherwise specified.

If multiple valid, nonmissing, categorical measurements exist on the same nominal visit, records will be chosen based on the following rule if a single value if needed:

- For baseline, the last available record on or prior to the first dose of study drug will be selected. If there are multiple records with the same time or no time recorded on the same day, the value with the lowest severity will be selected (eg, normal will be selected over abnormal for safety ECG findings).
- For postbaseline visits, the value for the scheduled visit only will be used. If multiple records are available for a scheduled visit, the most conservative value within that day will be selected (eg, abnormal will be selected over normal for safety ECGs).

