### **6.3. Other Efficacy Analyses**

#### **6.3.1. Definition of the Other Efficacy Endpoints**

Other efficacy endpoints include the following:

- Change, percentage change and fold change from baseline in the levels of serum cytokines (including IFN- $\alpha$ , IL-1RA, IP-10, and ITAC)
- Fold change in mRNA for ISGs including MX1, OAS1 and ISG15
- Change and percentage change from baseline in CD4/CD38/HLADR, CD8/CD38/HLADR and NK cell activation

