#### **6.3.2. Analysis of Other Efficacy Endpoints**

The full analysis set will be used for other efficacy endpoint analysis.

Change percentage change and fold change from baseline (postbaseline/baseline) in the levels of serum cytokines will be summarized by treatment group using descriptive statistics and compared between each active treatment group and the pooled placebo group using a Wilcoxon rank sum test at a two-sided 0.05 significant level.

Fold change from baseline (postbaseline/baseline) in mRNA for ISGs will be analyzed similarly as above.

Change and percentage change from baseline in CD4/CD38/HLADR, CD8/CD38/HLADR and NK cell activation will also be analyzed similarly as above.

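### SAP 3.3 bars covariates, so the biomarker comparisons with placebo give up precision for analytes that are quantifiable at Day 1 and only weakly to moderately correlated with it

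*SAP*

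**What the plan says.** SAP 3.3 says the randomisation is unstratified and then sets a general rule: "No covariates will be included in analyses".

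One secondary objective (SAP 1.1) is a pharmacodynamic comparison, "as measured by changes in interferon-stimulated genes (ISGs) and serum cytokines in whole blood compared to placebo". Immune-cell activation is a separate secondary objective.

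SAP 6.3.1 defines the cytokine endpoint as "Change, percentage change and fold change from baseline in the levels of serum cytokines". SAP 6.3.2 says these are "compared between each active treatment group and the pooled placebo group using a Wilcoxon rank sum test at a two-sided 0.05 significant level". The other two marker families follow the same route: "Fold change from baseline (postbaseline/baseline) in mRNA for ISGs will be analyzed similarly as above", and "Change and percentage change from baseline in CD4/CD38/HLADR, CD8/CD38/HLADR and NK cell activation will also be analyzed similarly as above".

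Under SAP 3.8.3, "the baseline value will be the last nonmissing value on or prior to the first dosing date of study drug". Protocol 6.2.3 schedules that sample for every cohort: "Whole blood ISG mRNA panel" stands in the Day 1 blood list, together with serum for cytokines and whole blood for immune-cell activation.

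**The concern.** A change score assumes that the post-dose value moves one-for-one with the Day 1 value. When the true slope is below 1, subtracting the whole baseline over-corrects and carries baseline noise into the outcome. A model that estimates the slope removes that noise, and the data for it are already scheduled.

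Each dose group has 6 subjects. These comparisons are how the trial would recognise a biologically active dose, so avoidable imprecision makes an active dose easier to miss. SAP 6.3.2 also plans p-values and group summaries but no estimate of the difference from placebo with a confidence interval.

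**Working it through.** **Inputs.** SAP 1.2: 6 active and 2 placebo subjects per cohort. SAP 3.2: placebo pooled over six cohorts, 6 × 2 = 12, giving seven analysis groups and 6 × 8 = 48 subjects. SAP 6.3.2: two-sided 0.05. Neither document gives an effect size, an SD or r, and neither has a power calculation, so there is no planned figure to reproduce. r is an assumption, shown over a range. Fold change and log fold change have the same ranks, so the log scale represents the fold-change endpoints.

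**1. Variance.** Take equal variances before and after dosing. The change-score variance is proportional to 2(1 − r) and the baseline-adjusted variance to 1 − r², so their ratio is (1 + r)/2. Estimating the slope costs a factor 1 + 1/(N − g − 2), where N is the number of subjects and g the number of groups in the model. The factor is 1 + 1/39 for N = 48, g = 7, and 1 + 1/14 for a pairwise model with N = 18, g = 2.

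| r | (1 + r)/2 | Seven-group model | Pairwise 6 v 12 |
|---|---|---|---|
| 0.3 | 0.65 | 0.67 | 0.70 |
| 0.5 | 0.75 | 0.77 | 0.80 |
| 0.7 | 0.85 | 0.87 | 0.91 |
| 0.9 | 0.95 | 0.97 | 1.02 |

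Break-even is at r = 2/(1 + 1/39) − 1 = 0.95 for the seven-group model and 2/(1 + 1/14) − 1 = 0.87 for the pairwise model.

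**2. Power from the covariate alone.** Assume an effect of 1.15 SD of the change score. At 6 v 12 the standard error is √(1/6 + 1/12) = 0.5 SD, so the noncentrality is 1.15/0.5 = 2.3. Dividing by the square root of the seven-group ratio gives 2.82, 2.62, 2.46 and 2.33 at the four values of r. A seven-group model on log change has about 61% power at every r. Adding log baseline to the same model gives about 79%, 72 to 73%, 67% and 62%. Simulation with equal-variance normal data agrees. The covariate is worth about 17, 10 to 11, 6 and 1 points.

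**3. Visits with fewer placebo subjects.** The count of 12 applies only where all six cohorts are sampled. For immune activation the only shared post-dose day is Day 3 (Protocol 6.3.1, 6.3.3 and 6.4). For ISGs and cytokines the shared days include Days 3, 57, 59 and 64. At visits belonging only to Cohorts 1 to 3 or only to Cohorts 4 to 6, such as Days 2, 58 and 127 to 134, pooled placebo is 3 × 2 = 6. (Around Dose 4, Cohort 6 joins Cohorts 1 to 3 for ISGs and cytokines if it escalates, giving 4 × 2 = 8.) At 6 v 6 the standard error is √(1/6 + 1/6) = 0.58 SD. For the same effect, a four-group model on change has 47 to 48% power. Adding baseline gives 64%, 56%, 51% and 47% at r = 0.3, 0.5, 0.7 and 0.9.

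**4. Unequal spread.** Suppose residual SDs of 1, 1, 1, 1.3, 1.6 and 2 across rising doses and 1 for placebo (an assumption), with no true effect. A common-variance ANCOVA over all groups then rejects 13 to 15% of the time at the top dose, a pairwise ANCOVA 10.5 to 12%, and the planned Wilcoxon test 6 to 8%.

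**The case against.** The strongest reply is that the plan is a defensible choice for exploratory endpoints. Protocol 8.1.4 lists these markers as other endpoints of interest, and the protocol synopsis plans only descriptive summaries. There is no power calculation, and SAP 6 asks for cautious interpretation. A rank test is robust at 6 per group, and step 4 shows that a common-variance ANCOVA is less protected at the top dose, where wider spread is plausible because Protocol 1.2.3.1 reports dose-dependent responses. This stands. It is why the adjusted model should support the Wilcoxon test and not replace it.

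Four stronger readings are tempting, and the documents do not support them.

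- **Every comparison loses precision.** This depends on an unstated r. The gain is about nil near r = 0.9, and a pairwise model loses slightly there. It is also about nil for an analyte mostly below quantitation before dosing, because SAP 3.7 sets such values to the LLOQ and the covariate becomes nearly constant. That is plausible for IFN-α, which Protocol 1.4 reports as undetectable in most earlier hepatitis patients, but it is not shown for this population.
- **The Day 1 value is discarded.** It is built into every endpoint. Only the gain beyond the change score is lost.
- **The comparisons are biased.** Under randomisation a change score is unbiased. Chance baseline imbalance is sampling error, and simulated Wilcoxon type I error under equal variance was about 4%.
- **The whole gap between the Wilcoxon test and ANCOVA is due to the covariate.** Part of it comes from swapping a rank test for a parametric one and from pooling residual variance over seven groups. For the effect in step 2 the Wilcoxon test has 51 to 53% power and the unadjusted seven-group model about 61%, before any covariate is added.

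**Conclusion.** The point holds as one of efficiency. For analytes quantifiable at Day 1 with low to moderate r, SAP 3.3 shuts out an analysis with about two-thirds to seven-eighths of the change-score variance (r from 0.3 to 0.7, seven-group model), using samples already scheduled. At 6 v 12 that is worth about 17 power points at r = 0.3, falling to about 1 at r = 0.9. Absolute power is lower where placebo is 6.

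These sizes rest on an assumed r, equal variance before and after dosing, approximate normality on the log scale and an assumed effect of 1.15 SD of change. None of these is in the documents. The plan contains no contradiction here, and its main test can stand.

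**What to change.** 1. In SAP 3.3, limit the sentence so that it does not cover the biomarkers in section 6.3.
2. In SAP 6.3.2, keep the Wilcoxon test as the main test. Add a supportive ANCOVA of log post-dose value on treatment group and log Day 1 value, at each visit, over all groups sampled at that visit. Report the adjusted ratio to placebo with its 95% CI.
3. Let residual variance differ by group. SAP 8.3.2 already uses PROC MIXED with Kenward-Roger degrees of freedom, which can be adapted. With 6 per group, check its error rate by simulation first. The alternative is a pairwise model checked for unequal spread.
4. Define quantifiable at baseline before the final unblinding, from Day 1 data pooled over arms. One option is no more than 25% of values below quantitation, borrowing the lowest percentage cut-off that SAP 3.7 uses for displaying BLQ concentrations.

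Settle this before the final analysis, because SAP 2.1.2 records that selected sponsor staff have already seen unblinded interim biomarker data.

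The cost is SAP wording and a few lines of code; no new samples are needed. The statistical price is one degree of freedom, a log-normal assumption, and possible anti-conservative error at the top dose if unequal variance is ignored.
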